## **7.0 Recruitment Plan**

Patients will be offered the opportunity to participate in this trial if they have the diagnosis of a CNS/leptomeningeal solid tumor (including neuroblastoma, small cell lung cancer, melanoma, retinoblastoma, high grade astrocytoma, medulloblastoma, central nervous system PNET, malignant glioma ependymoma, rhabdoid tumors, osteosarcoma, DSRCT and other tumors that are GD2-positive) and fulfilled the eligibility criteria. The opportunity to participate will be offered to all patients, including women and minority groups. Informed consent will be obtained from the patients or their legal guardians by an investigator authorized to obtain consent. Patient will not receive any payment for their participation in this study.

## **8.0 Pretreatment Evaluation**

8.1 Complete history, physical exam, and detailed neurologic exam.

8.2 CBC with differential and platelet count.

8.3 Serum electrolytes, creatinine, AST, total bilirubin, TSH, HAMA, and in child-bearing females, beta-HCG.

8.4 CSF cytology, total protein, glucose and cell count (these are baseline routine, not for research purposes), HAMA.

8.5 Baseline MRI of the brain and spine (with and without gadolinium) within 3 weeks of the first injection.

8.6  $^{111}\text{Indium Ommaya}$  patency/CSF flow study prior to the first injection.

## **9.0 Treatment/Intervention Plan**

9.1 General outline: Following an initial test dose of 2 mCi  $^{131}\text{I}$ -3F8 for dosimetry, four weekly injections will be given via an Ommaya reservoir that will be placed by neurosurgery if not already present. If the patient has a ventriculoperitoneal shunt, and CSF flow study using the

shunt tubing has confirmed acceptable CSF flow, the shunt may be used for the administration of  $^{131}\text{I}$ -3F8. Patients can be treated in an outpatient setting or may be hospitalized overnight for supportive care after each injection. All patients will be monitored in accordance with Radiation Safety Guidelines. Patients are not anticipated to need isolation post-treatment.

## 9.2 Premedications for $^{131}\text{I}$ -3F8

The following pre-medication guidelines are strongly suggested, but may be altered based on the clinical judgment of the investigators without being considered a protocol violation.

To start about 5 days prior to the test dose with  $^{131}\text{I}$ -3F8:

SSKI: 7 drops daily (to begin 5 days pre- injection and to continue for 2 weeks after the last injection)

Liothyronine (Liothyronine): 25 mcg/day if weight less than 25 kg, 50 mcg/day if weight greater or equal to 25 kg (to begin 5 days pre-injection and to continue for 2 weeks after the last injection)

To start 1-2 days prior to each injection:

Dexamethasone (for those patients not already on a higher dose of dexamethasone): 0.5 mg po bid if weight less than 15 kg, 1 mg po bid if weight greater than or equal to 15 kg (to begin about 24 hours pre-injection and to be tapered over ~1 week)

To be started about 1 to 2 hours before each injection:

Hydroxyzine (Vistaril): 1 mg/kg IV, then Q 4 hours x 24 hours post-injection (maximum 50 mg).

Acetaminophen (Tylenol): 10 mg/kg po before injection and then Q4 hours x 24 hours post-injection (maximum 325 mg)

Lorazepam (Ativan): 0.05 mg/kg IV x 1 (maximum 1mg)

Hydromorphone (Dilaudid): 0.015 mg/kg/dose x 1, then PRN (maximum 1mg)

### 9.2.1 Intraventricular administration of all drugs

The antibody 3F8 is radiolabeled with iodogen method under the supervision of Dr. [name] and [name] according to the FDA requirements specified by the IND. All patients will have an intraventricular reservoir (i.e. Ommaya reservoir). The Ommaya catheter site will be prepped and draped. A volume of CSF equal to the volume of drug to be injected will be removed, the drug will be injected slowly so as not to exceed a rate of 1ml/min. Sterile HSA will be flushed into the reservoir followed by autologous CSF flush. After  $^{131}\text{I}$ -3F8 dosimetry injections, patients will have approximately 0.5 cc CSF and 1-2 cc blood obtained for radioactivity levels at approximately, 1 hr, 2 hr, 4-6 hr, 18-24 hr, 44-48 hr, 66-72 hr and ~5-7 days post injection.

## 9.3 Treatment and dosimetry

### **9.3.1 \* Dose adjustments for age <3 years based on CSF volume:**

< 1 year: 50% dose reduction

1-3 years: 33% dose reduction

>3 years: Full dose, 10 mCi  $^{131}\text{I}$ -3F8 per injection

+averaging approximately 5 mCi of radioiodine/mg 3F8

### **\* Dose adjustments for patients with prior craniospinal radiation:**

The total maximum target CSF dose by  $^{131}\text{I}$ -3F8 injections will be 2400 Gy for patients with prior craniospinal radiation based on  $^{131}\text{I}$ -3F8/ scintigraphy dosimetry estimates. This may require a decrease or elimination of the 3rd or 4th injection to prevent the risk of radiation toxicity for these patients.

### **9.3.2 Dosimetry will be assessed by**

\*CSF and blood (2 ml/sample) obtained for radioactivity levels at approximately, and 1, 2, 4, 18, and 44 hours after  $^{131}\text{I}$ -3F8 dosimetry injection. (CSF samples obtained here are for research purposes). At the time of  $^{131}\text{I}$ -3F8 scintigraphy analysis, routine dosimetry estimations will be derived from the serial scintigraphy studies at approximately 4, 24, and 48 hours.

Pharmacokinetic data obtained from scintigraphy will be used in conjunction with direct counting of CSF and blood samples in a well scintillation counter, and combined with MRI anatomical imaging to estimate the absorbed dose to brain, CSF space, blood and visible tumor nodules.

## **9.4 Tumor genetic studies**

9.4.1 Tumor DNA and matched normal DNA will be used for genomic DNA sequencing, copy number analysis and methylation profiling; tumor RNA will be used for transcriptome and microRNA profiling. The samples will not have any associated patient-specific identifying information, but will be linked to clinical information such as patient age, gender, tumor stage, tumor recurrence status, and tumor site. The identity of individual patients will be kept in a secure database registered with the Office of Clinical Research, under the supervision of [name] according to HIPAA regulations. This testing will be done in [name] (Z740). These tests will be done only on the tumor left over after testing for 3F8 binding.

9.4.2 Immunohistochemical profile: Frozen tumors will be collected to be tested for tissue antigens and gangliosides [including but not limited to GM2, GD2, GD3]. These tests will only be done on patients whose tumors are not known to bind to 3F8, and therefore are consented to the assessment arm of the protocol.

## **10.0 Evaluation During Treatment/Intervention**

### **10.1 Evaluation during treatment**

10.1.1. Physical exam prior to each injection and after the 4th injection

10.1.2. Neurologic exam prior to each injection and after the 4th injection

- 10.1.3. MRI of head and spine at baseline and after 4th injection
- 10.1.4. CSF Flow study prior to the first injection
- 10.1.5. CBC with differential including platelets prior to each injection and ~1-3 months after 4th injection
- 10.1.6. Comprehensive profile to each injection and ~1-3 months after 4th injection.  
 \*Thyroid protection such as SSKI and Cytomel will be adjusted to ensure adequate thyroid saturation. Serum HAMA (send to [name]) prior to each injection.
- 10.1.7. B-HCG for females of child-bearing age prior to injections 1 and 3.
- 10.1.8. CSF and Blood (2 ml each sample) at ~1-4 hr, 18-24 hours, and 42-48 hours after the I-3F8 dosimetry injection

Observation	Prior to test dose with  I-3F8	Post test dose with  I-3F8	Prior to 1st injection	Post 1 st  I-3F8 Injection	Prior to 2 nd  I-3F8 injection	Post 2 nd injection	Prior to 3 rd  I-3F8 injection	Post 3 rd injection	Prior to 4 th  I-3F8 injection	Follow-up, 1-3 months after 4 th injection
Physical examination	X		X		X		X		X	X
Neurologic examination	X		X		X		X		X	X
MRI head	X									X
MRI spine	X									X
CSF flow study	X									
CBC w/diff, plts	X		X		X		X		X	X
Comprehensive profile	X		X		X		X		X	X
CSF cytology	X									X
Serum HAMA	X		X		X		X		X	
B-HCG (when applicable)	X						X			
Scintigraphy imaging  I-3F8		X								
CSF and Blood (2ml/sample)  I-3F8	X									

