## **4.1 Overview of Study/Design Intervention**

### **4.2 Design**

This is a phase II single-arm open-label study that will define responses to therapy with weekly intrathecal  $^{131}\text{I}$ -3F8 in patients with central nervous system/leptomeningeal GD2-expressing disease. Dosimetry at plaques of disease and surrounding normal tissues will be determined by a pre-treatment  $^{131}\text{I}$ -3F8 (2 mCi) scintigraphy. Pharmacokinetics of the dosimetry

dose of intrathecal  $^{131}\text{I}$ -3F8 will be determined by measurements of counts per minute (cpm) of serial CSF and serum samples.

Patients will then receive intrathecal  $^{131}\text{I}$ -3F8 treatment cycle (10 mCi/cycle) approximately weekly for a total of 4 cycles. A total dose of 40 mCi  $^{131}\text{I}$ -3F8 will be administered. Since the phase I study demonstrated a CSF dose of 15-60 cGy/mCi to the CSF, maximum total anticipated CSF dose of  $4 \times 10$  mCi of  $^{131}\text{I}$ -3F8 injections would be 600-2400 cGy; dose to the spinal cord and normal brain is negligible given the short range path length of  $^{131}\text{I}$ . At an estimated tumor to CSF dose ratio of 5:1, tumor dose could be as high as 3000-12000 cGy. Myelosuppression is not anticipated at this dose level. The chosen 40 mCi maximum  $^{131}\text{I}$  dose is considerably lower than the MTD reported using other intrathecal  $^{131}\text{I}$ -monoclonal antibodies for neoplastic meningitis on other phase I studies. To avoid the risk of radiation toxicity in patients who have had previous craniospinal radiation, the CSF radiation dose delivered by  $^{131}\text{I}$ -3F8 therapy injections will not exceed 2400 cGy based on the CSF dosimetry estimates from pre-treatment  $^{131}\text{I}$ -3F8 / scintigraphy scans. This may require the elimination and/or dose reduction of the 3rd or 4th injection for patients who have had previous craniospinal radiation. There will be no dose modifications for patients who have not had craniospinal radiation. Response to therapy will be assessed by neurologic examination, radiographic imaging and CSF cytology analysis. Other aims will be met by monitoring patients clinically and biochemically for toxicity and by serum assessment of HAMA.

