## 11.0 Toxicities/Side Effects

11.1 Toxicities will be assessed via the NCI toxicity criteria (CTC 3.0). All toxicities will be recorded in CRDB until 30 days after the last dose of  $^{131}\text{I}$ -3F8.

11.2 Toxicities associated with  $^{131}\text{I}$ -3F8 include fever, headache, nausea and vomiting, pain, allergic reaction, and/or drug extravasation. Hospitalizations for therapy administration, hyperglycemia or lymphopenia related to dexamethasone and self-limited fever, vomiting, or headache will not be considered serious adverse events (SAE) and will not be reported to the IRB or FDA though they will be captured in the institutional database. However, life-threatening infections or other life-threatening side effects will be considered SAE's and will be promptly reported to the Institutional Review Board of MSKCC and to the FDA.

11.3 Neurologic changes during the study period which meet the criteria for grade 4 neurotoxicity will be assessed by study physicians as being unrelated, possibly or probably caused by the injection. In the absence of clear evidence of tumor progression, it may be assumed that new signs and symptoms are treatment related.

11.4 Any deaths will be reviewed during the study by the Principal Investigators prior to subsequent entry of further patients.

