### **17.2 Serious Adverse Event (SAE) Reporting**

An adverse event is considered serious if it results in ANY of the following outcomes:

- Death
- A life-threatening adverse event
- An adverse event that results in inpatient hospitalization or prolongation of existing hospitalization
- A persistent or significant incapacity or substantial disruption of the ability to conduct normal life functions
- A congenital anomaly/birth defect
- Important Medical Events (IME) that may not result in death, be life threatening, or require hospitalization may be considered serious when, based upon medical judgment, they may jeopardize the patient or subject and may require medical or surgical intervention to prevent one of the outcomes listed in this definition

Note: Hospital admission for a planned procedure/disease treatment is not considered an SAE.

SAE reporting is required as soon as the participant signs consent. SAE reporting is required for 30-days after the participant's last investigational treatment or intervention. Any events that occur after the 30-day period and that are at least possibly related to protocol treatment must be reported.

If an SAE requires submission to the IRB office per IRB SOP RR-408 „Reporting of Serious Adverse Events“, the SAE report must be sent to the IRB within 5 calendar days of the event. The IRB requires a Clinical Research Database (CRDB) SAE report be submitted electronically to the SAE Office as follows:

Reports that include a Grade 5 SAE should be sent to [[contact]](mailto:[contact]). All other reports should be sent to [[contact]](mailto:[contact]).

The report should contain the following information:

Fields populated from CRDB:

- Subject's initials
- Medical record number
- Disease/histology (if applicable)
- Protocol number and title

Data needing to be entered:

- The date the adverse event occurred
- The adverse event
- The grade of the event
- Relationship of the adverse event to the treatment (drug, device, or intervention)
- If the AE was expected
- The severity of the AE
- The intervention
- Detailed text that includes the following
  - A explanation of how the AE was handled
  - A description of the subject's condition
  - Indication if the subject remains on the study
- If an amendment will need to be made to the protocol and/or consent form

- If the SAE is an Unanticipated Problem

The PI's signature and the date it was signed are required on the completed report.

For IND/IDE protocols:

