#### 17.2.1 Reporting Guidelines:

- Patient Consented/registered on the assessment part only: NO SAEs will be reported
- Patient Consented/registered on the treatment part:

All SAEs will be reported to the FDA through the IND office with reference to the IND # BB-IND-2299

**SAEs will be defined as grade 4 and 5 toxicities excluding: hospitalizations for therapy administration, hyperglycemia or lymphopenia related to dexamethasone and self-limited fever, vomiting, or headache will not be considered serious adverse events (SAE) and will not be reported to the IRB or FDA**

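### Toxicity recording closes at day 30, before nearly all of the 1-3 month laboratory window, and TSH is not named after baseline

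*Combined protocol and SAP*

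**What the plan says.** Section 2.1 lists the cumulative toxicity of serial injections as the third objective. Section 4.2 (Design) says how it is to be met: "Other aims will be met by monitoring patients clinically and biochemically for toxicity". No tests are listed there. Section 14.0 says toxicities will be reported by type and grade.

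Three places govern what is measured and kept:

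- **Pretreatment (8.3).** The blood list begins "Serum electrolytes, creatinine, AST, total bilirubin, TSH, HAMA". This is the only place where TSH is named.
- **During and after treatment (10.1.6 and the schedule table).** The repeated chemistry is "Comprehensive profile to each injection and ~1-3 months after" the 4th injection. Its components are not given. A starred note under the same item says thyroid protection will be adjusted to keep the gland saturated, with no test, threshold or time.
- **Recording (11.1).** "All toxicities will be recorded in CRDB until 30 days after the last dose of" the study agent.

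Section 17.2, on serious adverse events, adds: "Any events that occur after the 30-day period and that are at least possibly related to protocol treatment must be reported". Section 17.2.1 then narrows the term for the treatment part: "SAEs will be defined as grade 4 and 5 toxicities excluding" certain expected events.

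The thyroid is recognised as an organ to protect. Section 4.3 (Intervention) gives SSKI and liothyronine for that purpose. Section 9.2 suggests SSKI "to begin 5 days pre- injection and to continue for 2 weeks after the last injection", and the same duration for liothyronine.

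**The concern.** A cumulative-toxicity aim depends most on what is seen after the last injection. The plan schedules one laboratory visit for that, then closes the toxicity record at about the day the visit window opens. If 11.1 is followed exactly, a mild or moderate abnormality found at that visit need not be graded or counted. The report for the third objective could then look clean because of the recording rule.

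The thyroid is the clearest example. The agent carries radioiodine, the plan gives drugs to keep it out of the gland, and a baseline TSH is taken. Without a stated repeat and a rule to record it, the baseline has nothing assured to be compared with.

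**Working it through.** The plan states no figure on this point, so there is none to reproduce. The check is one timing calculation and a side-by-side reading.

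**1. Overlap of the visit window with the recording period**

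Inputs: recording closes at day 30 after the last dose (11.1). The visit is at 1 to 3 months after the 4th injection (10.1.6 and the table). Day 0 is the last injection, which is the 4th for a patient who completes treatment. The length of a month, m, is assumed to be 28, 30 or 30.4 days.

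Formulas: window = m to 3m; width = 2m; overlap = max(0, 30 - m); share = overlap / width.

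| m (days) | Window (day) | Overlap (days) | Width (days) | Share |
|---|---|---|---|---|
| 28 | 28 to 84 | 30 - 28 = 2 | 56 | 2/56 = 3.6% |
| 30 | 30 to 90 | 30 - 30 = 0 (boundary day only) | 60 | 0% |
| 30.4 | 30.4 to 91.2 | 0 | 60.8 | 0% |

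At the late end the visit falls up to 91.2 - 30 = 61.2 days after recording closes. The share is of days in the window, not of patients. The plan gives the timing as approximate, so a somewhat early visit could fall inside.

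**2. What is scheduled inside the recording period**

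The profiles before injections 2, 3 and 4 fall inside it, so effects of earlier injections can be recorded. After the 4th injection, the next scheduled chemistry is the 1-3 month visit. Unscheduled findings up to day 30 would be recorded.

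**3. Patients who stop early**

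Section 12.1 counts two injections as an adequate trial, and section 9.3 may drop the 3rd or 4th after craniospinal radiation. The visit is timed from the 4th injection, so for these patients it has no stated date.

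**4. Whether 17.2 fills the gap**

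The sentence on events after 30 days schedules no test and sits under serious-event reporting. With 17.2.1 limiting serious events to grades 4 and 5, it does not clearly reach a low-grade laboratory change.

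**5. Whether the profile includes TSH**

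The 8.3 blood list has seven items: electrolytes, creatinine, AST, bilirubin, TSH, HAMA and beta-HCG. In the table, HAMA and beta-HCG have their own rows, and the other five have none. The profile row is the only place left for them, and the thyroid note is attached to the same item. Inclusion is therefore plausible but never stated. Dosimetry does not substitute: section 9.3.2 estimates dose to brain, CSF space, blood and visible tumor, not to the thyroid.

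**6. Whether a TSH at that visit would be readable**

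On the suggested schedule liothyronine stops at day 14. The visit is then m - 14 to 3m - 14 days later: 14 to 70, 16 to 76, or 16.4 to 77.2 days. Section 9.2 says the premedication "may be altered based on the clinical judgment of the investigators without being considered a protocol violation", so the actual stop date may differ. I assume, as general pharmacology not taken from the documents, that thyroid hormone intake lowers TSH. Current use therefore has to be recorded with the result.

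**The case against.** The strongest reply is that TSH is probably already in the repeated profile. The table has no other row for the 8.3 chemistries, and by a strict reading creatinine, AST and bilirubin would not be required after baseline either, which is hardly intended. This stands. It reduces the TSH part to an undefined term and leaves the recording rule as the main point, because that rule causes the same gap whether or not TSH is measured.

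A second reply is that the investigators do look beyond day 30. The preliminary phase II results in section 3.4 report no late toxicity in 5 patients in remission off therapy for at least a year. Section 16.0 says collected data go into a secure database. Both are fair, and a reader should not infer that results after day 30 are discarded. But neither section requires a late abnormality to be graded, and section 3.4 names no thyroid test.

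Third, the yield is limited. One early test cannot exclude later hypothyroidism, and in a single arm with prior craniospinal radiation in some patients, attribution is uncertain. That stands, and it limits what may be claimed from the result.

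**Conclusion.** The point holds as a minor one. Followed as written, 11.1 leaves non-serious abnormalities from the only scheduled post-treatment laboratory visit almost entirely outside the toxicity record: 0 to 3.6% of the window's days overlap, for a month of 28 to 30.4 days. This assumes that visits are spread over the window; actual visit dates are not given. Separately, the text does not settle whether TSH is repeated after baseline.

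A reader might infer three stronger things, none of which the documents support:

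- **That thyroid function is not checked after baseline.** The table layout and the note under 10.1.6 point the other way; it is only not assured.
- **That thyroid injury has occurred or been missed at some rate.** The available text gives no thyroid dose, event rate or number tested, so no rate can be stated or bounded.
- **That the efficacy conclusion is affected.** The primary endpoint is survival at six months and the two-stage rule counts survivors; neither uses these data.

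**What to change.** 1. Amend 11.1 so that toxicities found at the 1-3 month visit are recorded and graded (CTC 3.0) despite the 30-day limit.
2. Define the repeated profile, and name TSH explicitly in the table at baseline and at the 1-3 month visit.
3. Time that visit from the last injection given, so that patients who stop before the 4th are covered.
4. Record with the TSH result whether thyroid hormone is being taken and whether there was prior craniospinal radiation.
5. Report the number tested, change from baseline and grade, split by prior craniospinal radiation, and describe the result as early change only.

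Section 14.0 describes the overall analysis as complete, so the change would apply to whichever of the 36 + 36 + 18 + 18 = 108 added evaluable places are still open. The documents do not say how many.

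The cost is one assay per patient, usually on blood already drawn, one table row, two data fields and one sentence in 11.1. Patients who stop early would need a draw scheduled. Attribution remains limited in a single arm.

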### 10.3 Pharmacokinetic Studies

Study of the intrathecal pharmacokinetics and blood pharmacokinetics of the I-3F8 dosimetry dose will be performed. Patients will have approximately 0.5cc of CSF obtained pre-injection, 1 hr, 2 hr, 4-6 hr, 18-24 hr, and 42-48 hr post injection. Blood samples (2 cc of plasma) will be obtained at the time of CSF sampling, and may be obtained via a central venous catheter (if present) or an indwelling heparin lock venous catheter. Additional samples may be collected if needed to adequately characterize pharmacokinetics. Radioactivity will be counted in a gamma counter. The count information will be used for pharmacokinetic data.

